Vomiting	Transient or intermittent vomiting with no or minimal interference with oral intake	Frequent episodes of vomiting with no or mild dehydration	Persistent vomiting resulting in orthostatic hypotension OR Aggressive rehydration indicated	Life-threatening consequences (eg, hypotensive shock)

NEUROLOGICAL				
	Grade 1	Grade 2	Grade 3	Grade 4
Alteration in Personality-Behavior or in Mood (eg, agitation, anxiety, depression, mania, psychosis)	Alteration causing no or minimal interference with usual social & functional activities	Alteration causing greater than minimal interference with usual social & functional activities	Alteration causing inability to perform usual social & functional activities	Behavior potentially harmful to self or others (eg, suicidal/homicidal ideation or attempt, acute psychosis) OR Causing inability to perform basic self-care functions
Altered Mental Status For Dementia, see Cognitive and Behavioral/Attentional Disturbance (including dementia and ADD)	Changes causing no or minimal interference with usual social & functional activities	Mild lethargy or somnolence causing greater than minimal interference with usual social & functional activities	Confusion, memory impairment, lethargy, or somnolence causing inability to perform usual social & functional activities	Delirium OR obtundation, OR coma
Ataxia	Asymptomatic ataxia detectable on exam OR Minimal ataxia causing no or minimal interference with usual social & functional activities	Symptomatic ataxia causing greater than minimal interference with usual social & functional activities	Symptomatic ataxia causing inability to perform usual social & functional activities	Disabling ataxia causing inability to perform basic self-care functions
Cognitive and Behavioral/Attentional Disturbance (including dementia and Attention Deficit Disorder)	Disability causing no or minimal interference with usual social & functional activities OR Specialized resources not indicated	Disability causing greater than minimal interference with usual social & functional activities OR Specialized resources on part-time basis indicated	Disability causing inability to perform usual social & functional activities OR Specialized resources on a full-time basis indicated	Disability causing inability to perform basic self-care functions OR Institutionalization indicated
CNS Ischemia (acute)	NA	NA	Transient ischemic attack	Cerebral vascular accident (CVA, stroke) with neurological deficit
Developmental delay – Pediatric ≤ 16 Years	Mild developmental delay, either motor or cognitive, as determined by comparison with a developmental screening tool appropriate for the setting	Moderate developmental delay, either motor or cognitive, as determined by comparison with a developmental screening tool appropriate for the setting	Severe developmental delay, either motor or cognitive, as determined by comparison with a developmental screening tool appropriate for the setting	Developmental regression, either motor or cognitive, as determined by comparison with a developmental screening tool appropriate for the setting

NEUROLOGICAL				
	Grade 1	Grade 2	Grade 3	Grade 4
Headache	Symptoms causing no or minimal interference with usual social & functional activities	Symptoms causing greater than minimal interference with usual social & functional activities	Symptoms causing inability to perform usual social & functional activities	Symptoms causing inability to perform basic self-care functions OR Hospitalization indicated (other than ER visit) OR Headache with significant impairment of alertness or other neurologic function
Insomnia	NA	Difficulty sleeping causing greater than minimal interference with usual social/functional activities	Difficulty sleeping causing inability to perform usual social & functional activities	Disabling insomnia causing inability to perform basic self-care functions
Neuromuscular Weakness (including myopathy & neuropathy)	Asymptomatic with decreased strength on exam OR Minimal muscle weakness causing no or minimal interference with usual social & functional activities	Muscle weakness causing greater than minimal interference with usual social & functional activities	Muscle weakness causing inability to perform usual social & functional activities	Disabling muscle weakness causing inability to perform basic self-care functions OR Respiratory muscle weakness impairing ventilation
Neurosensory Alteration (including paresthesia and painful neuropathy)	Asymptomatic with sensory alteration on exam or minimal paresthesia causing no or minimal interference with usual social & functional activities	Sensory alteration or paresthesia causing greater than minimal interference with usual social & functional activities	Sensory alteration or paresthesia causing inability to perform usual social & functional activities	Disabling sensory alteration or paresthesia causing inability to perform basic self-care functions
Seizure: (new onset)	NA	1 seizure	2–4 seizures	Seizures of any kind that are prolonged, repetitive (eg, status epilepticus), or difficult to control (eg, refractory epilepsy)

NEUROLOGICAL				
	Grade 1	Grade 2	Grade 3	Grade 4
Seizure: (pre-existing) For Worsening of Existing Epilepsy the Grades Should Be Based on an Increase from Previous Level of Control to Any of These Levels	NA	Increased frequency of pre-existing seizures (non-repetitive) without change in seizure character OR infrequent breakthrough seizures while on stable meds in a previously controlled seizure disorder	Change in seizure character from baseline either in duration or quality (eg, severity or focality)	Seizures of any kind that are prolonged, repetitive (eg, status epilepticus), or difficult to control (eg, refractory epilepsy)
Seizure – Pediatric < 18 Years	Seizure, generalized onset with or without secondary generalization, lasting < 5 minutes with < 24 hours post ictal state	Seizure, generalized onset with or without secondary generalization, lasting 5–20 minutes with < 24 hours post ictal state	Seizure, generalized onset with or without secondary generalization, lasting > 20 minutes	Seizure, generalized onset with or without secondary generalization, requiring intubation and sedation
Syncope (not associated with a procedure)	NA	Present	NA	NA
Vertigo	Vertigo causing no or minimal interference with usual social & functional activities	Vertigo causing greater than minimal interference with usual social & functional activities	Vertigo causing inability to perform usual social & functional activities	Disabling vertigo causing inability to perform basic self-care functions

MUSCULOSKELETAL				
	Grade 1	Grade 2	Grade 3	Grade 4
Arthralgia See also Arthritis	Joint pain causing no or minimal interference with usual social & functional activities	Joint pain causing greater than minimal interference with usual social & functional activities	Joint pain causing inability to perform usual social & functional activities	Disabling joint pain causing inability to perform basic self-care functions
Arthritis See also Arthralgia	Stiffness or joint swelling causing no or minimal interference with usual social & functional activities	Stiffness or joint swelling causing greater than minimal interference with usual social & functional activities	Stiffness or joint swelling causing inability to perform usual social & functional activities	Disabling joint stiffness or swelling causing inability to perform basic self-care functions
Bone Mineral Loss Pediatric < 21 Years	BMD t-score or z-score -2.5 to -1.0 BMD z-score -2.5 to -1.0	BMD t-score or z-score < -2.5 BMD z-score < -2.5	Pathological fracture (including loss of vertebral height) Pathological fracture (including loss of vertebral height)	Pathologic fracture causing life-threatening consequences Pathologic fracture causing life-threatening consequences
Myalgia (non-injection site)	Muscle pain causing no or minimal interference with usual social & functional activities	Muscle pain causing greater than minimal interference with usual social & functional activities	Muscle pain causing inability to perform usual social & functional activities	Disabling muscle pain causing inability to perform basic self-care functions
Osteonecrosis	NA	Asymptomatic with radiographic findings AND No operative intervention indicated	Symptomatic bone pain with radiographic findings OR Operative intervention indicated	Disabling bone pain with radiographic findings causing inability to perform basic self-care functions

SYSTEMIC				
	Grade 1	Grade 2	Grade 3	Grade 4
Acute Systemic Allergic Reaction	Localized urticaria (wheals) with no medical intervention indicated	Localized urticaria with medical intervention indicated OR Mild angioedema with no medical intervention indicated	Generalized urticaria OR Angioedema with medical intervention indicated OR Symptomatic mild bronchospasm	Acute anaphylaxis OR Life-threatening bronchospasm OR laryngeal edema
Chills	Symptoms causing no or minimal interference with usual social & functional activities	Symptoms causing greater than minimal interference with usual social & functional activities	Symptoms causing inability to perform usual social & functional activities	NA
Fatigue Malaise	Symptoms causing no or minimal interference with usual social & functional activities	Symptoms causing greater than minimal interference with usual social & functional activities	Symptoms causing inability to perform usual social & functional activities	Incapacitating fatigue/malaise symptoms causing inability to perform basic self-care functions
Fever (nonaxillary)	37.7°C to 38.6°C 99.8°F to 101.5°F	38.7°C to 39.3°C 101.6°F to 102.8°F	39.4°C to 40.5°C 102.9°F to 104.9°F	> 40.5°C > 104.9°F
Pain- Indicate Body Site See also Injection Site Pain, Headache, Arthralgia, and Myalgia	Pain causing no or minimal interference with usual social & functional activities	Pain causing greater than minimal interference with usual social & functional activities	Pain causing inability to perform usual social & functional activities	Disabling pain causing inability to perform basic self-care functions OR Hospitalization (other than ER visit) indicated
Unintentional Weight Loss	NA	5% to 9% loss in body weight from baseline	10% to 19% loss in body weight from baseline	≥ 20% loss in body weight from baseline OR Aggressive intervention indicated [eg, tube feeding or total parenteral nutrition]

INJECTION SITE REACTION				
	Grade 1	Grade 2	Grade 3	Grade 4
Injection Site Pain (pain without touching) Or Tenderness (pain when area is touched)	Pain/tenderness causing no or minimal limitation of use of limb	Pain/tenderness limiting use of limb OR Pain/tenderness causing greater than minimal interference with usual social & functional activities	Pain/tenderness causing inability to perform usual social & functional activities	Pain/tenderness causing inability to perform basic self-care function OR Hospitalization (other than ER visit) indicated for management of pain/tenderness
Injection Site Reaction (Localized), > 15 Years Pediatric ≤ 15 Years	Erythema OR Induration of 5 × 5 cm to 9 × 9 cm (or 25–81 × cm ²) Erythema OR Induration OR Edema present but ≤ 2.5 cm diameter	Erythema OR Induration OR Edema > 9 cm any diameter (or > 81 cm ²) Erythema OR Induration OR Edema > 2.5 cm diameter but < 50% surface area of the extremity segment (eg, upper arm/thigh)	Ulceration OR Secondary infection OR Phlebitis OR Sterile abscess OR Drainage Erythema OR Induration OR Edema involving ≥ 50% surface area of the extremity segment (eg, upper arm/thigh) OR Ulceration OR Secondary infection OR Phlebitis OR Sterile abscess OR Drainage	Necrosis (involving dermis and deeper tissue) Necrosis (involving dermis and deeper tissue)
Pruritis Associated with Injection See also Skin: Pruritis (itching—no skin lesions)	Itching localized to injection site AND Relieved spontaneously or with < 48 h treatment	Itching beyond the injection site but not generalized OR Itching localized to injection site requiring ≥ 48 h treatment	Generalized itching causing inability to perform usual social & functional activities	NA

ENDOCRINE/METABOLIC				
	Grade 1	Grade 2	Grade 3	Grade 4
Lipodystrophy (eg, back of neck, breasts, abdomen)	Detectable by study participant or caregiver (for young children and disabled adults)	Detectable on physical exam by health care provider	Disfiguring OR Obvious changes on casual visual inspection	NA
Diabetes Mellitus	NA	New onset without need to initiate medication OR Modification of current meds to regain glucose control	New onset with initiation of indicated med OR Diabetes uncontrolled despite treatment modification	Life-threatening consequences (eg, ketoacidosis, hyperosmolar non-ketotic coma)
Gynecomastia	Detectable by study participant or caregiver (for young children and disabled adults)	Detectable on physical exam by health care provider	Disfiguring OR Obvious on casual visual inspection	NA
Hyperthyroidism	Asymptomatic	Symptomatic causing greater than minimal interference with usual social & functional activities OR Thyroid suppression therapy indicated	Symptoms causing inability to perform usual social & functional activities OR Uncontrolled despite treatment modification	Life-threatening consequences (eg, thyroid storm)
Hypothyroidism	Asymptomatic	Symptomatic causing greater than minimal interference with usual social & functional activities OR Thyroid replacement therapy indicated	Symptoms causing inability to perform usual social & functional activities OR Uncontrolled despite treatment modification	Life-threatening consequences (eg, myxedema coma)
Lipoatrophy (eg, fat loss from the face, extremities, buttocks)	Detectable by study participant or caregiver (for young children and disabled adults)	Detectable on physical exam by health care provider	Disfiguring OR Obvious on casual visual inspection	NA

GENITOURINARY				
	Grade 1	Grade 2	Grade 3	Grade 4
Intermenstrual Bleeding (IMB)	Spotting observed by participant OR Minimal blood observed during clinical or colposcopic exam	Intermenstrual bleeding not greater in duration or amount than usual menstrual cycle	Intermenstrual bleeding greater in duration or amount than usual menstrual cycle	Hemorrhage with life-threatening hypotension OR Operative intervention indicated
Urinary Tract obstruction (eg, stone)	NA	Signs or symptoms of urinary tract obstruction without hydronephrosis or renal dysfunction	Signs or symptoms of urinary tract obstruction with hydronephrosis or renal dysfunction	Obstruction causing life-threatening consequences

INFECTION				
	Grade 1	Grade 2	Grade 3	Grade 4
Infection (any other than HIV infection)	Localized, no systemic antiꞑbial treatment indicated AND Symptoms causing no or minimal interference with usual social & functional activities	Systemic antiꞑbial treatment indicated OR Symptoms causing greater than minimal interference with usual social & functional activities	Systemic antiꞑbial treatment indicated AND Symptoms causing inability to perform usual social & functional activities OR Operative intervention (other than simple incision and drainage) indicated	Life-threatening consequences (eg, septic shock)

Basic Self-care Functions: Activities such as bathing, dressing, toileting, transfer/movement, continence, and feeding.

Usual Social & Functional Activities: Adaptive tasks and desirable activities, such as going to work, shopping, cooking, use of transportation, pursuing a hobby, etc.

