1.4. Rationale for Dose Selection of SOF/VEL/VOX FDC

SOF/VEL (400/100 mg) once daily is the approved marketed dose and, as such, was selected for co-formulation with VOX into a fixed dose combination tablet. The VOX 100 mg dose was selected based on the anti-HCV activity of VOX established in the Phase 1b proof-of-concept study GS-US-338-1121 and Phase 2 studies in subjects with HCV infection (GS-US-367-1169 and GS-US-367-1168). These studies indicated that the voxilaprevir exposures achieved following administration of VOX 100 mg + SOF/VEL (400/100 mg) with food are associated with > 90% of the maximum antiviral response across all HCV genotypes.

The combination of SOF 400 mg, VEL 100 mg, and VOX 100 mg has been administered in Phase 2 and Phase 3 studies to over 1900 subjects. SOF/VEL/VOX FDC (400/100/100 mg) tablet was evaluated in the registrational Phase 3 POLARIS program and these doses represent the marketed dose of SOF/VEL/VOX FDC tablet for the treatment of HCV-infection in adults.

Sofosbuvir is a substrate for efflux drug transporters P-glycoprotein (P-gp) and breast cancer resistance protein (BCRP). SOF is extensively metabolized to the pharmacologically active nucleoside analog phosphate. The activation pathway involves hydrolysis by intestinal and hepatically expressed carboxylesterase (CES1) and Cathepsin A (CatA) enzymes {[Yang 2009](#), [Zhu 2009](#)}. SOF is also converted to GS-331007, an inactive circulating metabolite, which is eliminated renally by active tubular secretion and glomerular filtration.

Velpatasvir is also a substrate for P-gp and BCRP. VEL has low systemic clearance in nonclinical species and low metabolic turnover by Cytochrome P450 2B6 (CYP2B6), Cytochrome P450 2C8 (CYP2C8) and Cytochrome P450 3A4 (CYP3A4). It is eliminated through biliary excretion as unchanged parent drug and metabolites (76.6% of the administered dose is recovered as VEL in feces).

Voxilaprevir is a substrate for P-gp, BCRP, and Organic Anion-Transporting Polypeptide (OATP) 1B1/3. VOX has low in vitro turnover, primarily by CYP3A4. It is eliminated through biliary excretion as unchanged parent drug and metabolites (40% of the administered dose is recovered as VOX in feces).

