4.3. Exclusion Criteria

Subjects who meet *any* of the following exclusion criteria are not to be enrolled in this study.

- 1) Current or prior history of clinical hepatic decompensation (eg, clinical ascites, encephalopathy, and/or variceal hemorrhage)
- 2) Any of the following laboratory parameters at Screening:
 - a) INR >1.2 x ULN
 - b) Platelets < 50,000/mm³
 - c) Albumin < 3.5 g/dL
 - d) ALT > 10 x ULN
 - e) AST > 10 x ULN
 - f) Direct bilirubin > 1.5 x ULN
 - g) Estimated glomerular filtration rate < 90 mL/min/1.73m², as calculated by the Schwartz formula
- 3) Chronic liver disease of a non-HCV etiology (eg, hemochromatosis, Wilson's disease, alpha-1 antitrypsin deficiency)
- 4) Evidence of hepatocellular carcinoma or other malignancy (with exception of certain resolved skin cancers)
- 5) Co-infection with human immunodeficiency virus (HIV), acute hepatitis A virus (HAV) or hepatitis B virus (HBV) (hepatitis B surface antigen [HBsAg] positive at Screening)
- 6) Current or prior history of any of the following:
 - a) Clinically significant illness (other than HCV) or any other major medical disorder that may have interfered with subject treatment, assessment, or compliance with the protocol; subjects currently under evaluation for a potentially clinically significant illness (other than HCV) are also excluded
 - b) Significant cardiac disease
 - c) Gastrointestinal malabsorption syndrome that may interfere with absorption of orally administered medications
 - d) History of solid organ or bone marrow transplantation

- e) Psychiatric hospitalization, suicide attempt, and/or a period of disability as a result of their psychiatric illness within the last 5 years. Subjects with psychiatric illness (without the prior mentioned conditions) that is well controlled on a stable treatment regimen for at least 6 months prior to enrollment or has not required medication in the last 12 months may be included
- 7) Clinically relevant alcohol or drug abuse within 12 months of Screening. A positive drug screen will exclude subjects unless it can be explained by a prescribed medication; the diagnosis and prescription must be approved by the investigator
- 8) Use of any prohibited concomitant medications as described in Section 5.3.
- 9) Investigational agents taken within the past 28 days (except with the approval of the sponsor)
- 10) Known hypersensitivity to the study drug, the metabolites, or formulation excipients

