6.8.11. Estimated Glomerular Filtration Rate (GFR)

Estimated Glomerular Filtration Rate (GFR) using Schwartz Formula ($\text{mL}/\text{min}/1.73\text{m}^2$) = $k \times L/\text{Scr}$ [(k is a proportionality constant, for adolescent females ≥ 12 years old is 0.55; and for adolescent males ≥ 12 years old is 0.70); L is height in centimeters (cm); and S_{cr} is serum creatinine (mg/dL)]

CCI

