Infant, ≤ 14 Days (non-hemolytic)	NA	20.0 to 25.0 mg/dL 342 to 428 μmol/L	> 25.0 to 30.0 mg/dL > 428 to 513 μmol/L	> 30.0 mg/dL > 513 μmol/L
Infant, ≤ 14 Days (hemolytic)	NA	NA	20.0 to 25.0 mg/dL 342 to 428 μmol/L	> 25.0 mg/dL > 428 μmol/L
Blood Urea Nitrogen	1.25 to 2.50 × ULN	> 2.50 to 5.00 × ULN	> 5.00 to 10.00 × ULN	> 10.00 × ULN
Hyperuricemia	>ULN to 10.0 mg/dL >ULN to 597 μmol/L	> 10.0 to 12.0 mg/dL > 597 to 716 μmol/L	> 12.0 to 15.0 mg/dL > 716 to 895 μmol/L	> 15.0 mg/dL > 895 μmol/L
Hypouricemia Adult and Pediatric ≥ 1 year	1.5 mg/dL to < LLN 87 μmol/L to < LLN	1.0 to < 1.5 mg/dL 57 to < 87 μmol/L	0.5 to < 1.0 mg/dL 27 to < 57 μmol/L	< 0.5 mg/dL < 27 μmol/L
Infant < 1 Year	N/A	1.0 mg/dl to <LLN- 57 μmol to <LLN	0.5 to < 1.0 mg/dL 27 to < 57 μmol/L	< 0.5 mg/dL < 27 μmol/L

CHEMISTRY				
	Grade 1	Grade 2	Grade 3	Grade 4
Creatinine**	> 1.50 to 2.00 mg/dL > 133 to 177 µmol/L	> 2.00 to 3.00 mg/dL > 177 to 265 µmol/L	> 3.00 to 6.00 mg/dL > 265 to 530 µmol/L	> 6.00 mg/dL > 530 µmol/L
Bicarbonate Adult and Pediatric ≥ 4 Years	16.0 mEq/L to < LLN 16.0 mmol/L to < LLN	11.0 to < 16.0 mEq/L 11.0 to < 16.0 mmol/L	8.0 to < 11.0 mEq/L 8.0 to < 11.0 mmol/L	< 8.0 mEq/L < 8.0 mmol/L
Pediatric < 4 Years	NA	11.0 mEq/L to <LLN 11.0 mmol/L to <LLN	8.0 to < 11.0 mEq/L 8.0 to < 11.0 mmol/L	< 8.0 mEq/L < 8.0 mmol/L
Triglycerides (Fasting)	NA	500 to 750 mg/dL 5.64–8.47 mmol/L	> 750 to 1200 mg/dL > 8.47–13.55 mmol/L	> 1200 mg/dL > 13.55 mmol/L
LDL (Fasting) Adult	130 to 160 mg/dL 3.35 to 4.15 mmol/L	>160 to 190 mg/dL >4.15 to 4.92 mmol/L	> 190 mg/dL >4.92 mmol/L	NA
LDL (Fasting) Pediatric >2 to <18 years	110 to 130 mg/dL 2.84 to 3.37 mmol/L	>130 to 190 mg/dL >3.37 to 4.92 mmol/L	> 190 mg/dL >4.92 mmol/L	NA
Hypercholesterolemia (Fasting)	200 to 239 mg/dL 5.16 to 6.19 mmol/L	> 239 to 300 mg/dL > 6.19 to 7.77 mmol/L	> 300 mg/dL > 7.77 mmol/L	NA
Pediatric < 18 Years	170 to 199 mg/dL 4.39 to 5.15 mmol/L	> 199 to 300 mg/dL > 5.15 to 7.77 mmol/L	> 300 mg/dL > 7.77 mmol/L	NA
Creatine Kinase	3.0 to < 6.0 × ULN	6.0 to < 10.0 × ULN	10.0 to < 20.0 × ULN	≥ 20.0 × ULN

* Calcium should be corrected for albumin if albumin is < 4.0 g/dL

** An overlap between the Grade 1 scale and the Lab's normal range for creatinine may result for Male subjects >70 yrs. Please follow the Gilead convention of grading any result within the LLN and ULN a 0.

ENZYMES				
	Grade 1	Grade 2	Grade 3	Grade 4
AST (SGOT)	1.25 to 2.50 × ULN	> 2.50 to 5.00 × ULN	> 5.00 to 10.00 × ULN	> 10.00 × ULN

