7.2.1. Summaries of Numeric Laboratory Results

Descriptive statistics (n, mean, SD, median, Q1, Q3, minimum, and maximum) will be provided for ALT, aspartate aminotransferase (AST), total bilirubin, alkaline phosphatase, hemoglobin, reticulocytes, white blood cell (WBC), neutrophils, lymphocytes, platelets, and international normalized ratio (INR) as follows:

- Baseline values
- Values at each postbaseline analysis window
- Change from baseline at each postbaseline analysis window

A baseline laboratory value will be defined as the final assessment performed on or prior to the date/time of first dose of study drug. Change from baseline to a postbaseline visit will be defined as the visit value minus the baseline value. The mean, median, Q1, Q3, minimum, and maximum will be displayed to the reported number of digits; SD to the reported number of digits plus 1.

Median (Q1, Q3) of the observed values for these laboratory parameters will be plotted using a line plot by visit.

In the case of multiple values in an analysis window, data will be selected for analysis as described in Section 3.7.3 (Selection of Data in the Event of Multiple Records in a Window).

The number of subjects with hemoglobin < 10 g/dL and < 8.5 g/dL at any postbaseline visits (up to 30 days after the last dose of any study drug) will be summarized.

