7.2.2. Graded Laboratory Values

The Gilead Grading Scale for Severity of Adverse Events and Laboratory Abnormalities will be used for assigning toxicity grades to laboratory results for analysis as Grade 0, Grade 1, Grade 2, Grade 3, or Grade 4. Grade 0 includes all values that do not meet the criteria for an abnormality of at least Grade 1. Some laboratory tests have criteria for both increased and decreased levels; analyses for each direction (ie, increased, decreased) will be presented separately.

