7.2.2.1. Treatment-Emergent Laboratory Abnormalities

Treatment-emergent laboratory abnormalities are defined as values that increase at least 1 toxicity grade from baseline at any postbaseline time point, up to and including the date of last dose of study drug plus 30 days for subjects who permanently discontinued study drug. If the relevant baseline laboratory value is missing, then any abnormality of at least Grade 1 will be considered treatment emergent.

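### After baseline, creatinine is tabulated only by grades that start above 1.50 mg/dL, so an empty table is weak evidence of renal safety in adolescents

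*Protocol*

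**What the plan says.** **Grading.** Protocol Appendix 3 (Chemistry) grades creatinine on a single absolute scale, with Grade 1 at "> 1.50 to 2.00 mg/dL". There is no pediatric row and no baseline-relative criterion. The only footnote on overlap with the normal range concerns men over 70. The same appendix has pediatric rows for phosphate, LDL, cholesterol and albumin, and a decrease-from-baseline criterion for hemoglobin.

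**Counting.** SAP 7.2.2 states that "Grade 0 includes all values that do not meet the criteria for an abnormality of at least Grade 1". SAP 7.2.2.1 counts as treatment-emergent only "values that increase at least 1 toxicity grade from baseline at any postbaseline time point".

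**Numeric summaries.** SAP 7.2.1 begins "Descriptive statistics (n, mean, SD, median, Q1, Q3, minimum, and maximum) will be provided for ALT, aspartate aminotransferase (AST), total bilirubin, alkaline phosphatase" and goes on to hemoglobin, reticulocytes, white cells, neutrophils, lymphocytes, platelets and INR. That makes 11 analytes; creatinine and eGFR are not among them.

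**eGFR.** Protocol 4.3 excludes subjects with "Estimated glomerular filtration rate < 90 mL/min" per 1.73m2, "as calculated by the Schwartz formula". SAP 5.2 lists eGFR as a baseline characteristic. Neither document plans a post-baseline eGFR analysis.

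**Data collected.** Creatinine is in the chemistry panel (Protocol 6.8.1), which Protocol Appendix 2 schedules at every on-treatment visit and at posttreatment Week 4. Height is measured at each visit (Protocol 6.8.5).

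**The concern.** For creatinine, the planned post-baseline tables record only whether a value exceeded 1.50 mg/dL. Everything below that is Grade 0, whatever the subject's baseline. If that limit sits well below normal renal function for a 12 to 17 year old, a clean table is compatible with a substantial fall in eGFR.

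Safety is a secondary objective. Renal function also bears on the study's pharmacology: Protocol 1.4 says of GS-331007, one of the four primary PK analytes, "which is eliminated renally by active tubular secretion and glomerular filtration". The risk is that a line in the study report showing no graded creatinine abnormality is read as reassurance about kidney function that the table cannot give.

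**Working it through.** The plan states no figure to reproduce here, so the check is whether the grade threshold is informative on the protocol's own eGFR scale.

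**Inputs from the documents**
- eGFR = k × L / Scr, with L in cm and Scr in mg/dL. The constant k "for adolescent females ≥ 12 years old is 0.55; and for adolescent males ≥ 12 years old is 0.70" (Protocol 6.8.11; repeated in SAP 5.2). SAP 2.2 limits the final analysis to adolescents, so these two constants suffice.
- Highest creatinine that is still Grade 0: 1.50 mg/dL.
- Lowest eligible eGFR at Screening: 90 mL/min/1.73m2.

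**Assumptions (not in the documents)**
- Heights of 140 to 180 cm.
- Baseline eGFR of 90 (the entry limit), 120 or 150.
- Height constant between the two measurements.

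**Is the threshold a typing error?** Appendix 3 gives paired units. 133/1.50 = 88.7, 177/2.00 = 88.5, 265/3.00 = 88.3 and 530/6.00 = 88.3. The pairs agree, so 1.50 mg/dL is what the scale intends.

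**Step 1: eGFR at the Grade 0 limit.** eGFR = k × L / 1.50. For example, a 140 cm girl gives 0.55 × 140 / 1.50 = 51.3, and a 180 cm boy gives 0.70 × 180 / 1.50 = 84.0.

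**Step 2: largest loss still Grade 0.** Loss = 1 − (eGFR at 1.50) / (baseline eGFR), which at constant height equals 1 − (baseline Scr) / 1.50. For example, a 170 cm boy from 120 gives 1 − 79.3/120 = 33.9%, and a 150 cm girl from 120 gives 1 − 55.0/120 = 54.2%.

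| Subject | eGFR at 1.50 mg/dL | Loss from 90 | Loss from 120 | Loss from 150 |
|---|---|---|---|---|
| Girl 140 cm | 51.3 | 43.0% | 57.2% | 65.8% |
| Girl 150 cm | 55.0 | 38.9% | 54.2% | 63.3% |
| Girl 160 cm | 58.7 | 34.8% | 51.1% | 60.9% |
| Girl 170 cm | 62.3 | 30.7% | 48.1% | 58.4% |
| Girl 180 cm | 66.0 | 26.7% | 45.0% | 56.0% |
| Boy 140 cm | 65.3 | 27.4% | 45.6% | 56.4% |
| Boy 150 cm | 70.0 | 22.2% | 41.7% | 53.3% |
| Boy 160 cm | 74.7 | 17.0% | 37.8% | 50.2% |
| Boy 170 cm | 79.3 | 11.9% | 33.9% | 47.1% |
| Boy 180 cm | 84.0 | 6.7% | 30.0% | 44.0% |

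**Step 3: the same loss by baseline creatinine.** Loss = 1 − Scr/1.50 gives 66.7% at 0.5 mg/dL, 50.0% at 0.75, 40.0% at 0.9 and 33.3% at 1.0. Losing half therefore requires a baseline of 0.75 mg/dL or less. At exactly 0.75, the baseline eGFR is 0.55 × 160 / 0.75 = 117 for a 160 cm girl and 0.70 × 170 / 0.75 = 159 for a 170 cm boy.

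Every value in the second column is below 90. Over this range of heights, a subject can fall below the study's own entry limit and contribute nothing to the graded table.

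**The case against.** **Individual cases are not hidden.** SAP 7.2 lists serum chemistry by subject and visit and flags values outside the reference range even when they are Grade 0. With a cohort planned at 20 or more, such a listing can be read. Protocol 7.1.3 requires abnormalities that need intervention or alter dosing to be recorded as adverse events, and SAP 7.1.6 tabulates adverse events. The data monitoring committee reviews safety data about every 6 months (Protocol 8.10). All of this stands. A reader might infer that renal harm would go undetected, and the documents do not support that. What listings do not give is a rate, a trend or a group change.

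**About half is not a general figure.** A reader might infer that any adolescent could lose about half of eGFR and remain Grade 0. That depends on a baseline the documents do not give. From an assumed eGFR of 120 it fits girls (45% to 57% over the assumed heights) but not boys of 150 to 180 cm (30% to 42%), and from 90 a 170 cm boy reaches Grade 1 after a 12% loss.

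**The exposure argument is limited.** Protocol 8.5 reports no clinically significant exposure-safety relationship over a broad range of GS-331007 exposure. GS-331007 is also measured directly and its AUCtau compared with adults. Renal elimination is not renal toxicity, and the documents describe no renal signal. This lowers the priority of the point but does not make the graded table more informative.

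**The SAP breaks no commitment.** Protocol 8.6.3 promises summaries of selected laboratory data without naming them, so the list of 11 complies. That is correct. Even so, the SAP goes beyond the grades for hemoglobin (counts below 10 and 8.5 g/dL, SAP 7.2.1) and for liver tests (SAP 7.2.2.3), and plans no equivalent for creatinine.

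**A count below 90 is crude.** It would flag someone who moves from 91 to 89 and miss a fall from 150 to 91. This stands, and it shapes the fix.

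**Conclusion.** The point holds as a cheap improvement to reporting. It is neither an error in the grading scale nor a conflict between protocol and SAP. Outside flagged listings and adverse event reports, the only post-baseline creatinine summary cannot register a change until creatinine exceeds 1.50 mg/dL. On the protocol's formula that corresponds to an eGFR of about 51 to 84 at 140 to 180 cm, against an entry limit of 90.

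The size depends on sex, height and an assumed baseline. The representative losses are about 12% (170 cm boy) and 35% (160 cm girl) from 90, and about 34% (170 cm boy) and 54% (150 cm girl) from 120. The threshold itself, the missing summaries and the formula come straight from the documents; only the heights and starting eGFR values are assumed.

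**What to change.** Leave Appendix 3 unchanged. In SAP 7.2.1:

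1. Add serum creatinine and Schwartz eGFR (constants as in SAP 5.2) to the list, with observed value, change and percent change from baseline at each post-baseline visit that has chemistry.
2. State which height enters each eGFR, for example the same-visit height or otherwise the most recent one. This is needed because at the 4-week follow-up SAP Table 3-2 uses Days 4 to 30 for laboratory data and Days 21 to 69 for height.
3. If a count of subjects with post-baseline eGFR below 90 is reported, keep it descriptive. Show each such subject's baseline eGFR, and report the largest percent decline for all subjects, so that trivial moves near 90 and large falls from a high baseline can be told apart.

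The cost is a few table rows and a small derivation, with no new samples or visits. Some subjects will be flagged through ordinary variation. Protocol 8.6.3 leaves the choice of analytes open, so no protocol amendment is needed. If the SAP is already final, the addition can be documented in the study report, as SAP Section 1 provides. No dose, stopping rule or clinical management changes.
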